HL	Healthy Lifestyles
ICF	International Council for Harmonisation
ICS	Inhaled corticosteroids
IEC	Institutional Ethics Committee
IMR	Inspiratory Muscle Rehabilitation
IRB	Institutional Review Board
ITT	Intention to treat
LAMA	Long-acting muscarinic antagonist
LTRA	Leukotriene Receptor Antagonist
m	Meter
Max	Maximum
MIP	Maximum Inspiratory Pressure
mm	Millimeter
MVPA	Moderate-Vigorous Physical Activity
BDI	Baseline Dyspnea Index
FWA	Federal-wide Assurance
DMC	Data Monitoring Committee
ACQ	Asthma Control Questionnaire
MOP	Manual of Procedures
NC	North Carolina

NIH	National Institute of Health
O2	Oxygen
PI	Principal Investigator
REB	Research Ethics Board
SAE	Serious adverse event
SAR	Suspected adverse reaction
SD	Standard Deviation
SUSAR	Suspected Unexpected Serious Adverse Reactions

[figure not shown]
PROTOCOL HISTORY OF CHANGES		
Version	Date	Summary of Changes
1.0	DD-MMM-2021	N/A Original protocol

PROTOCOL SYNOPSIS

Protocol Title:	BREATHE Fit: Inspiratory Muscle Rehabilitation in Children with Obesity to Promote Physical Activity
Phase:	Pilot
Product:	PrO2 IMR ™ trainer
Objectives:	
Primary: Demonstrate inspiratory muscle rehabilitation (IMR) as an acceptable add-on intervention in children with obesity.
 
Secondary:
 
 1. Demonstrate changes in inspiratory muscle functioning and dyspnea reporting following IMR. 2. Demonstrate changes in daily physical activity following IMR. 
Exploratory: Demonstrate changes in exercise capacity following IMR.

Study Design:	Single-center, randomized, SHAM-controlled, parallel assignment, double masked, interventional study.
Study Population:	
Inclusion Criteria
 
 1. Documented informed consent from legal guardian and assent from participant as appropriate. 2. Children 8 to 17 years of age with obesity (BMI $\geq 95^{\text{th}}$ percentile for age and sex) being seen at Duke Healthy Lifestyles clinic. 3. Participants (or parent/guardian) must have access to the internet and an approved smart device/computer. 4. Child must have a designated caregiver who expresses a commitment to encourage the participant to complete the study procedures. 5. Participant and legal guardian must speak and read English or Spanish. 
Exclusion Criteria
 
 6. Prior enrollment in an IMR program. 7. Contraindications for IMR including a history of recent lung surgery, recent pulmonary embolism, or history of recurrent spontaneous pneumothorax 8. Progressive neurological or neuromuscular disorders or need for chronic O₂ therapy.

	
9. Inability to complete baseline measurements in a satisfactory manner according to the judgment of the research coordinator or PI.
 
10. Current self-reported pregnancy or planning to become pregnant.
 
11. Body weight greater than 300 pounds.
 
12. Any condition in the opinion of the PI that would not allow safe conduct of study procedures (including IMR, MIP testing or step-test), such as a physical disability, recent musculoskeletal injury or illness, current and ongoing evaluation for undiagnosed cardiopulmonary or neurologic symptoms, undiagnosed chest pain, pneumothorax in the past 12 months, inner ear surgery in the past 12 months, or undiagnosed syncopal episodes.

Number of Participants:	Up to 30
Number of Sites:	1 site
Duration of Participation:	Planned participation will be approximately 56 days. Total participation may be up to 77 days.
Intervention:	
Intervention: Inspiratory Muscle Trainer at 75% of the participant's maximal inspiratory pressure (MIP). Target dose: 3 sets of 50 inspiratory breaths 3 times per week.
 
Sham comparator: Inspiratory Muscle Trainer at 15% MIP. Target dose: 3 sets of 50 inspiratory breaths 3 times per week.

Estimated start:	Q1 2022
Estimated time to complete enrollment	Q3-4 2022

SCHEMATIC/DESCRIPTION OF STUDY DESIGN

2. BACKGROUND INFORMATION AND SCIENTIFIC RATIONALE

2.1 Background Information

Improved management of obesity is an urgent public health need. Nearly 40% of US children and adolescents have a body mass index that markedly increases their risk for serious metabolic and cardiopulmonary sequelae. Current childhood obesity rates, for the first time in US history, predict a decline in life US expectancy. Importantly, childhood obesity is a key driver of health disparities in the US, with obesity disproportionately affecting African-American, Hispanic-Latino and Native American children. A key contributor to the sequelae of obesity is sedentariness. Thus, best practice in obesity management includes both reducing sedentariness and establishing durable increases in daily physical activity^{1,2}, however, attrition from planned exercise programs remains high.³ A key challenge to initiating and sustaining physical activity in children with obesity is the extreme dyspnea (breathlessness) they experience. This is due to the altered thoracic mechanics of obesity which lead to enhanced inspiratory muscle fatigue and dyspnea, with even modest physical activity (Figure 2A). Our group has confirmed that among adolescents, higher body mass index (BMI) associates with lower inspiratory muscle endurance ($r = -0.680$, $p=0.049$, $n=14$), and that this lower endurance correlates with more frequent dyspnea ($r = -0.672$, $p=0.023$, $n=12$). Treating obesity-related inspiratory muscle impairment and dyspnea is a promising approach to support physical activity in children with obesity, but is yet unproven.

Inspiratory muscle rehabilitation (IMR) is a promising approach to reduce obesity-related dyspnea and boost physical activity.

Pulmonary rehabilitation (in its various forms, including IMR) is a treatment cornerstone in adult medicine but is underutilized in pediatrics.⁴ In adults, IMR has been studied in healthy athletes^{5,6}, and

[figure not shown]

Figure 2 Mechanisms of action of (A) obesity leading to dyspnea and activity avoidance, and (B)

numerous lung⁷⁻¹⁰ and neuromuscular¹¹⁻¹³ diseases. In adults, IMR consistently improves inspiratory muscle function, reduces dyspnea and improves exercise tolerance.¹⁴⁻¹⁹ Adding IMR to an exercise training regimen in healthy young adults who were obese led to significant improvements in subjective ratings of dyspnea and objectively measured exercise capacity.²⁰ **IMR has not been sufficiently studied in children with obesity.** However, recently in our pilot work at Duke, children with obesity (and asthma) underwent the 'DHBS' pilot IMR trial (NCT03911206). Children ($n=11$) were randomized to IMR (3 sets of 50 reps, three times/week), exercise or usual care for 6 weeks. Ten of 11 completed all visits, and 11 reported wanting to continue IMR after the study. IMR improved mean maximum inspiratory pressures (MIP) (+34 cm H₂O, $p=0.014$) and improved exercise capacity measured by 6-minute walk distance (+115 meters) ($p=0.136$) compared to IMR. Based on these

data, we are highly encouraged that IMR will help children with obesity increase their physical activity (**Figure 2B**).

Duke Pediatrics is expertly equipped to advance IMR in Children with Obesity.

Duke Pediatrics' Healthy Lifestyles (HL) clinic, led by Co-I [name], treats >7000 children ages 8-17 with obesity each year (>35% Black, >20% Hispanic).²¹ Treatment includes intensive lifestyle counseling, community-based physical activity, pharmacotherapy, or weight-reduction surgery.²² As part of routine clinical monitoring, patients in HL complete measures of exercise capacity to assess physical activity gains, and have (as part of consented research) provided wearable accelerometers to track total daily activity (i.e. steps) and time achieving moderate to vigorous physical activity (MVPA).^{23,24} [name] has led or facilitated multiple research studies within the obesity clinic, with established protocols and regulatory processes for recruitment, consent, and follow up study visits.^{21,25-27} This collaboration between the Pediatric Pulmonary and Healthy Lifestyles clinical research teams focuses on a completely new area of research for the investigators (IMR) and provides a superior environment for studying impactful innovations in pediatric obesity.

Together, we propose **BREATHE Fit**, a randomized SHAM-controlled 6-week trial of inspiratory muscle rehabilitation in children aged 8-17 years with obesity enrolled in the Duke HL. **Primary research question:** *Is IMR an acceptable add-on intervention that promotes greater activity in children with obesity?* The **BREATHE Fit** trial will address the following aims:

Aim 1. Demonstrate the acceptability of IMR in children with obesity.

Hypothesis 1a (H1a). More than 80% of participants will be satisfied with active IMR at study completion. H1b. Total IMR adherence will be >80% of planned active IMR repetitions. H1c. Active IMR will not be associated with any serious adverse reactions.

Aim 2. Demonstrate changes in inspiratory muscle functioning and dyspnea reporting following IMR. H2a. IMR will significantly increase inspiratory strength (measured by mean change in MIP). H2b. IMR will reduce patient-reported retrospective dyspnea scores during activities of daily living.

Aim 3. Demonstrate changes in daily physical activity following IMR.

H3a. IMR will lead to reduced sedentary time, increased moderate-strenuous time and increased total daily activity measured by a wrist-worn continuous activity tracking monitor.

2.2 Potential Benefits

IMR is very likely to improve inspiratory muscle strength. These benefits in inspiratory muscle strength may reduce dyspnea (breathlessness) with daily activity and with exercise. In addition, IMR may improve exercise capacity and exercise tolerance. Although improvements in these outcomes are not guaranteed, improvements in general health, daily activity and weight loss are a possibility.

Conclusions drawn from this study may benefit children with obesity by adding to the understanding of how IMR affects breathing. All participants will have baseline lung function testing and will have their daily physical activity monitored.

2.3 Compensation

Participants will be fairly compensated for their time and effort. Successful completion of the study (visit 3) will result in a \$75 monetary payment (gift cards). In addition, participants will be gifted the Garmin Vivosmart 4 study activity tracker (retail value \$100) on visit 1. If participants do not complete the study, they will be asked to return the activity tracker and inspiratory muscle trainer. Participants will receive a \$25 gift card with the successful completion of visit 2, and \$50 gift card with the successful completion of visit 3.

VISIT #	COMPENSATION
V1	Garmin Vivosmart 4 study activity tracker (retail value \$100)
V2	\$25 Nike gift card
V3	\$50 Nike gift card

2.4 Potential Study Risks

2.4.1 Risks of inspiratory muscle training

The risk of inspiratory muscle training is minimum. Inspiratory muscle training is deep breathing exercises against a resistance. Risks are thought to be generally minimal and similar to daily living or routine exercise. No known systematic reports are known describing risks from IMR. However, patients will be advised that they may experience mild, self-limited dizziness, headache, or dyspnea.

2.4.2 Risks of maximal inspiratory pressure measurement

Inspiratory muscle strength testing is a routine clinical test performed in the outpatient setting. The side-effect profile is expected to be similar to that of inspiratory muscle training.

2.4.3 Risks of stair-step challenge

The stair-step challenge is a generally safe exercise procedure conducted in the outpatient setting. There is a small chance of tripping or falling during the procedure and possible resulting injury. Close supervision and spotting of the participant will take place to reduce the chance of injury.

2.4.4 Potential risk of loss of confidentiality

There is a potential risk of loss of confidentiality. Every effort will be made to protect the participant's confidential medical information, but this cannot be guaranteed.

2.4.5 Unforeseen risks

There may be other risks to the participant from this research that are not known or foreseeable at this time.

3. OBJECTIVES AND OUTCOME MEASURES

Table 1 Objectives and Outcomes Measures			
Primary Objectives	Outcome Measures	Endpoints	Analysis
Demonstrate IMR as an acceptable add-on intervention in children with obesity.	1. completion of study Visit 3 (V3) 2. adherence to active IMR 3. participant satisfaction among active IMR participants	1. prevalence of completer status 2. prevalence of IMR completion (actual / planned reps over intervention period) in active IMR group 3. prevalence of agree or strongly agree to question of satisfaction with active IMR	Simple descriptive statistics: calculation of prevalence
Secondary Objectives	Outcome Measures	Endpoints	Analysis
Demonstrate changes in inspiratory muscle functioning and dyspnea reporting following IMR	1. Maximum inspiratory pressure (MIP) 2. Baseline Dyspnea Index score 3. MRC breathlessness scale	1. change in MIP over intervention period 2. change in dyspnea scores over intervention period	Analysis of covariance (ANCOVA)
Demonstrate changes in daily physical activity following IMR	1. moderate-vigorous physical activity (MVPA) time 2. sedentary physical activity (SPA) time 3. total steps	1. change in average daily MVPA time 2. change in average daily SPA time 3. change in average daily step count	Analysis of covariance (ANCOVA)
Exploratory Objectives	Outcome Measures	Endpoints	Analysis
Demonstrate changes in exercise capacity following IMR	1. heart rate during 3 minute step test	1. heart rate change during 3-minute step test	Analysis of covariance (ANCOVA)

4. STUDY DESIGN

Overall Design

Single-center, randomized, SHAM-controlled, parallel assignment, double masked, interventional study.

4.1 Randomization

Participants (n=30) will be randomized to one of two treatment arms.

- Arm A (n=15): IMR
- Arm B (n=15): Sham

4.2 Blinding/Masking

Treatment assignment will be obtained through the Duke REDCap randomization system. All participant-facing study staff and participants will be blinded to the treatment assignment. Participants may come to feel that they can surmise whether their device is set to the active resistance. Although complete masking may not be possible in all participants, participants will only be informed that they are receiving one of two resistances (low or active). However, all study staff that assess outcomes (and the lead statistician) will remain blinded. Participants will be instructed to not discuss their presumed IMR assignment with study staff.

4.3 Study Interventions

Active IMR or SHAM using the PrO2™ device. Each participant will be provided a PrO2™ device and trained on its use as well as its accompanying PrO2 Fit™ app. The PrO2™ is a flow-resistive device that provides inspiratory resistance via a fixed 2mm orifice and has Bluetooth connectivity to most IOS/Android devices or Mac/Windows computers. The PrO2™ device and app allows for both 100% adherence monitoring and immediate user biofeedback.

Participants will be instructed at Visit 1 and Visit 2 to inspire forcefully through PrO2™ until the device signals that the user has achieved the target resistance (via audible alarm and visible light signal). The research team will implement biofeedback signals at a specific inspiratory resistance to provide precise and individualized training target. Successful IMR repetitions will require that subjects achieve a pressure target that is 75% of their MIP.

SHAM intervention. Participants in the control intervention will also use the same PrO2™ device but at a reduced peak resistance of 15% MIP. The research team will implement biofeedback signals at a specific inspiratory resistance to provide precise and individualized training target. Successful IMR repetitions will require that subjects achieve a pressure target that is 15% of their MIP.

Adherence monitoring. All device repetitions are automatically captured and documented via the Bluetooth connection with the PrO2™ app and end-to-end encrypted and transferred to a HIPAA-compliant cloud server (Amazon Web Services). Study staff will review each participant's adherence each week and will provide encouragement as needed.

4.4 Duration of Participation for Participant

The approximate duration of participation is 56 days. The maximum duration of participation will be 77 days.

4.5 Biological Specimen Testing

No biologic specimens will be taken.

4.6 Safety

See Section 8.

4.7 Events of Special Interest

Not applicable.

4.8 Rationale for Dose (inspiratory load) Selection

We used published IMR regimens to select an initial resistive load (intensity), number of repetitions/sets per day, and weekly session number for our pilot work (**Table 2**). We first completed an IRB-approved pilot study called the Duke Healthy Breathing Study 1(DHBS1) of directly supervised IMR in 10-17 year-olds with asthma. Using a commercially available IMR respiratory training device, participants with asthma completed and tolerated 4 sets of 60 reps of IMR at 60-75% MIP. We solicited feedback from both adolescents and parents regarding tolerability, acceptability, and future interest in IMR as a potential chronic breathing intervention. Nearly 95% of participants were able to complete all repetitions at 60-75% of MIP.

Table 2 Prior Duke IMR Projects

Investigator (year)	Population	IMR characteristics	Results
[name] (2017) DHBS1 (Duke funded)	14 children and adolescents (10-17 years of age) with persistent asthma	Repetitions: 4 sets of 50 inspirations	No significant AEs 100% acceptability 13 of 14 were interested in a home intervention
		Intensity: 60-75% MIP	
		Duration: 1 session	
[name] (2018-2020) DHBS2 (Duke funded)	Participants 10-17 years of age with persistent asthma and obesity or sedentariness	Dose: 1 session twice daily, 3 days/wk. Week 1: session= 1 set of 60 reps Week 2: session= 2 sets of 60 reps Week 3-6: session= 3 sets of 60 reps (with automated IMR monitoring)	11 subjects have completed 6-week intervention: 10/11 (91%) completed all visits 11 (100%) reported desire to continue IMR IMR treated participants showed non-significant improvements in inspiratory muscle strength/endurance, asthma control and exercise tolerance
		Intensity: 75% MIP	
		Duration: 6 weeks	

MIP – maximal inspiratory pressure, IMR – inspiratory muscle rehabilitation, AE – adverse event

This one-time session was well-tolerated in all participants without any significant adverse events. Thirteen of 14 (93%) participants wanted to continue daily IMR after study completion. Based on DHBS1, we initiated the DHBS2 study, an IRB-approved (NCT03911206) randomized, ‘usual care’-controlled, parallel-group, 6-

week intervention trial in which we tested the IMR regimen (75% MIP) in 10-17 year-olds with obesity and asthma.

Participants randomized to the IMR treatment completed 3 sets of 60 repetitions at

[figure not shown]

Figure 3 Change in validated asthma symptom scores with IMR. ACT – asthma control test, ACQ6 – asthma control questionnaire 6 item

75% MIP three days per week. Preliminary IMR findings from 11 participants involving changes in respiratory muscle strength and endurance, 6-minute walk distance and asthma symptom scores are encouraging and support the aims of this proposal (See **Figure 3** and **Table 3**). Adherence of IMR (n=6) was 79.2% of prescribed repetitions over 6 weeks, which is superior to published adherence rates (47-57%) for daily asthma controller drugs.

Table 3 Effects of Daily IMR treatment over 6 weeks on Respiratory Outcomes – Preliminary data

Outcome type	Intervention		p-value	Summary
	IMR (n=6)	No IMR (n=5)		
Asthma Symptoms: change in ACT, mean (SD) (for ACT, higher score means better asthma)	+1.0 (0)	-3.0 (2)	p=0.075	IMR-treated participants showed a near significant improvement in ACT compared to controls (Figure 3)
Asthma Symptoms: change in ACQ-6, Mean (SD) (for ACQ-6, lower score means better asthma)	-0.10 (0.56)	0.90 (0.90)	p=0.094	IMR-treated participants showed a near significant improvement in ACQ-6 compared to control (Figure 3)
Inspiratory muscle strength: change in baseline MIP (cm H ₂ O), mean (SD)**	+37.0 (24.1) ¹	+12.5 (16.4) ¹	p=0.128	IMR-treated participants showed near significant greater MIP improvement compared to controls
Inspiratory muscle strength: change in post-exercise MIP (cm H ₂ O), mean (SD)**	+14.6 (10.5) ²	-19.0 (19.9) ²	p=0.014	IMR-treated participants showed a significantly greater post-exercise MIP improvement compared to controls
Exercise tolerance: improvement in six-minute walk distance (meters), mean (SD)	119.1 (93.3)	4.0 (112.7)	p=0.136	IMR-treated participants showed non-significant improvement in

				6MW distance compared to controls
**two MIP measures were analyzed at each visit because of acute strengthening. ¹ – MIP1 start of visit (before exercise), ² – MIP2 end of visit (after exercise). ACQ-6 – score ranges from 0 to 6 with lower score meaning better asthma. Minimal important difference =0.4-0.5. ACT – score ranges from 6 to 30 with higher score meaning better asthma. Minimal important difference = 3				

4.9 Study Definition of Enrollment

A participant will be considered *enrolled* in the active study once eligibility criteria are satisfied, informed consent is signed, and the participant receives at least one dose of a study intervention (i.e. one training session).

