4.10 Study Definition of Completion

Participant study completion will be defined as a participant who has been enrolled and completes Visit 3.

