5.3. Screen Failures

Participants who sign informed consent but are not enrolled in the active study are considered screen failures and will be recorded in the Screen Failures area of the electronic data capture (EDC). Participants who do not initially satisfy eligibility requirements may be rescreened up to 2 additional times. Re-consent is not required for rescreened participants unless a revised version of the consent that requires re-consent is made available.

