5.5.6 Replacements

Females who become pregnant during the study will not receive further study intervention. In cases of early withdrawal, an additional participant may be enrolled.

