7.1.3 Product use and directions

Participants will be instructed to inspire forcefully through PrO2™ until the device signals that the user has achieved the target resistance (via audible alarm and visible light signal). The research team can implement biofeedback signals at a specific inspiratory resistance, which allows for a precise and individualized training target.

At Visit 1: Participants will download the PrO2™ Fit App from the Apple App Store or Google Play. They will be shown how to set up their own PrO2 Fit account and how to connect with their PrO2™ trainer. Research staff will review the planned dosing to start after visit 2. They will be instructed to try to avoid inferring what treatment assignment they have been given, and to not share any impressions they have developed on treatment assignment. The proper use of the trainer will be taught, including safe storage, cleaning and maintenance. Participants will be taught to create an air-tight seal over the mouthpiece after maximal exhalation. The participant will be instructed to breathe in forcefully until the device alarms then continue to maximal inspiration. At Visit 1, participants will be taught on the device while the alarm is set for 15% of their MIP. They will complete a set of 50 repetitions supervised so their technique is assessed and re-direction can occur if needed.

At Visit 2: participants will have refresher training on the use of the PrO2™ Fit app and will repeat their supervised single set of 50 repetitions while supervised to ensure they have the proper technique and the device is working properly.

Research staff will encourage participant and guardian to discuss a plan to optimize adherence to the IMR intervention. This may include picking particular days of the week (e.g. MWF, TuThS) and particular activities to link with IMR (e.g. in mornings before school, evenings before homework, etc.). Guardians will be asked to commit to helping the participant remember their intervention days.

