10.3 Analysis Population

All participants who are randomized and receive at least one IMR intervention will be included in the modified intention-to-treat (MITT) population.

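### A randomised child who receives no training session is classed as a screen failure and falls outside the only analysis population, so Aim 1 completion and adherence could be biased upward

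*Combined protocol and SAP*

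**What the plan says.** All references are to the combined protocol and SAP.

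- **Enrolment (4.9).** Besides eligibility and signed consent, the child must be one who "receives at least one dose of a study intervention (i.e. one training session". Randomisation is not mentioned.
- **Screen failure (5.3).** "Participants who sign informed consent but are not enrolled in the active study are considered screen failures". There is no exception for a child already randomised.
- **Completion (4.10).** "Participant study completion will be defined as a participant who has been enrolled and completes Visit 3".
- **Analysis population (10.3).** "All participants who are randomized and receive at least one IMR intervention will be included in the modified intention-to-treat (MITT) population". No other population is defined.
- **Primary endpoints (section 3, Table 1).** These include "prevalence of completer status" and "prevalence of IMR completion (actual / planned reps over intervention period) in active IMR group". Neither the table nor 10.2 states the denominator for completion. In 10.2, satisfaction is a percentage of completers, and serious adverse events are a percentage of those who had at least one active session.
- **Order of events (6.2.2).** Randomisation is step 7 of Visit 2 and device training is step 9. Section 6.2.3 (Continuation visit) lets an unfinished visit be completed within 14 days, or later if the PI approves.
- **Supervised practice (7.1.3).** At Visit 2 participants "will repeat their supervised single set of 50 repetitions while supervised". The prescribed session in 7.1.1 is three such sets. Section 7.1.3 also describes a supervised set at Visit 1, whereas Table 4 lists device training only at Visit 2.
- **Replacement (5.5.6).** "In cases of early withdrawal, an additional participant may be enrolled".

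**The concern.** When the question is whether children accept an intervention, not starting it after randomisation is itself an outcome. The four definitions together treat it as a reason to leave the trial. A non-starter cannot be a completer, contributes no planned repetitions, and is labelled as if randomisation had never happened. Removing such children can raise completion and adherence but cannot lower them. With 15 children planned per arm, one child is enough to move an arm-level percentage by several points. The exclusion also happens after randomisation, so the two arms compared under Aim 1 need not be the arms that were randomised.

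**Working it through.** **The plan's own figures.** The only design calculation is the power table (Table 5). All 24 cells reproduce with a two-sample t-test at two-sided 0.05 (largest difference 0.0005). This point does not depend on them.

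**Who can be lost.** The document does not define one training session, so there are two readings.

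1. The Visit 2 set of 50 counts. Only a child who leaves or refuses between steps 7 and 9 is lost, for example through a split Visit 2.
2. A full session of 3 × 50 is required. A child who does the clinic set and never trains at home is then also not enrolled.

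A third possibility shows how unsettled the wording is: if the Visit 1 set in 7.1.3 counted as a dose, a child would meet that part of 4.9 before randomisation. Section 7.1.3 and Table 4 must be reconciled.

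**Inputs**

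- Active arm: 15 (4.1 and 10.11).
- Planned repetitions per child: 3 × 50 × 3 per week × 6 weeks = 2,700 (7.1.1, six-week trial).
- Adherence hypothesis: more than 80% (10.1).
- Pilot adherence: 79.2%, n = 6 (4.8).
- Number of non-starters, k: not in the document; assumed 0 to 3.
- Mean adherence of starters: assumed 85% for illustration, with the pilot's 79.2% as an alternative.

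**Adherence.** Every child has the same planned total, so adherence over all randomised = starter mean × (15 − k)/15, with non-starters at zero. The starter mean needed to exceed 80% over all 15 is 80% × 15/(15 − k).

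| k | Starters only | Over all 15, starters at 85% | Over all 15, starters at 79.2% | Starter mean must exceed |
|---|---|---|---|---|
| 0 | 85% or 79.2% | 85.0% | 79.2% | 80.0% |
| 1 | 85% or 79.2% | 14 × 0.85/15 = 79.3% | 73.9% | 85.7% |
| 2 | 85% or 79.2% | 13 × 0.85/15 = 73.7% | 68.6% | 92.3% |
| 3 | 85% or 79.2% | 12 × 0.85/15 = 68.0% | 63.4% | 100% |

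With one non-starter, the exclusion changes the result against 80% only if the starter mean lies above 80% and at or below 85.7%. With two, the upper end is 92.3%. At 79.2% the hypothesis fails under either denominator.

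**A home refuser under reading 1.** Such a child stays in the analysis with 50/2,700 = 1.9% adherence. With 14 others at 85%, the arm is (14 × 0.85 + 0.0185)/15 = 79.5%. On that reading the plan already counts home refusal.

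**Completion.** Assume every starter completes and use exact 95% intervals.

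| k | Starters as denominator | All 15 as denominator |
|---|---|---|
| 1 | 14/14 = 100% (76.8 to 100) | 14/15 = 93.3% (68.1 to 99.8) |
| 2 | 13/13 = 100% (75.3 to 100) | 13/15 = 86.7% (59.5 to 98.3) |
| 3 | 12/12 = 100% (73.5 to 100) | 12/15 = 80.0% (51.9 to 95.7) |

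**The case against.** The strongest reply is that the route is narrow. Randomisation and device training belong to the same planned 60-minute visit, and that visit includes a supervised set. Sections 4.9 and 10.3 speak of receiving the intervention, not of completing a full session, so on the natural reading a child who does the clinic set stays in the analysis. The continuation described within 6.2.2 is for insufficient actigraphy and comes before randomisation; only the general continuation clause allows a split after step 7. This stands, and it limits the likely number of children lost. It does not remove the gap, because the session is undefined and nothing exempts a randomised child from 5.3.

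A reader might infer more than the document supports:

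- *That all children who refuse home training are removed.* This follows only if a full session is required.
- *That a completion target could falsely appear met.* There is none. The hypotheses set criteria for satisfaction, adherence and serious adverse reactions only.
- *That replacement deletes the child replaced.* Section 5.5.6 concerns early withdrawal and does not mention denominators. It is silent, not wrong.
- *That non-starters vanish from the report.* The CONSORT diagram in 10.8 would still show them, though only as disposition. The sensitivity analyses in 10.5 address missing Visit 3 primary outcomes, are conditional, and do not clearly reach children outside the analysis population.
- *That non-starters are clear refusals of the intervention.* A child lost before device training is masked and has not trained at the assigned load, so the reason may be logistical.

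It is also fair to say that excluding non-starters from the completion denominator is an inference, since that denominator is not written out. It is the inference that the only defined population invites.

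**Conclusion.** The point holds as a gap in the definitions. As written, a randomised child with no session is not enrolled, is filed as a screen failure, and lies outside the only analysis population, so completion and adherence could be biased upward. The size depends on a number the document does not give. In the illustration, one non-starter lowers adherence over all randomised from 85% to 79.3% and completion from 100% to 93.3%. The inputs of 85%, full completion among starters and one non-starter are all assumptions. With no non-starters the bias is zero. The document does not establish that bias will occur, or that the adherence conclusion will change. The change is worth making because it concerns primary endpoints and costs little.

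**What to change.** - In 4.9 and 4.10, make randomisation the point of enrolment. In 5.3, reserve screen failure for children who were not randomised.
- In sections 3, 10.2 and 10.3, state that Aim 1 completion and adherence are reported over all children randomised to the arm. A child who never trains counts as a non-completer with 0 of the planned repetitions.
- Keep the treated set for safety.
- State whether the supervised Visit 2 set counts as a training session, and reconcile 7.1.3 with Table 4 on device training at Visit 1.
- In 5.5.6, state that a child who is replaced stays in the denominators.

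The cost is wording. No new data are needed, because the device already records repetitions automatically (4.3). The downside is that reported completion and adherence may be slightly less favourable.
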